#### *iii.* Bias in the measurement of interventions (misclassification bias)

Bias in measurement of the interventions, i.e. the key surgical steps, will be minimised by the careful definition of these steps as achieved through Phase A of the CIPHER study (see

**Table 1Error! Reference source not found.**). These definitions have been applied when designing the electronic case report form (e-CRF) that will be completed with reference to the lead surgeon scrubbed at the time of stoma formation, before a participant leaves the operating theatre.

### *iv.* Bias due to departure from intended interventions (performance bias) Performance bias will be minimised by estimating the effects of the key surgical factors that were *intended* to be implemented [42].

#### v. Bias due to missing data (attrition bias)

Bias due to missing data will be minimised by using multiple methods to collect the data needed for the study (see 5.4), especially data relating to the follow-up of participants (see 5.4).

## vi. Bias in the measurement of outcomes (detection bias)

We do not expect measurements of patient-reported PSH symptoms and other patientreported outcomes (PROs) to be at risk of bias, since participants are unlikely to know the surgical methods used when forming the index stoma or the comparisons of interest; moreover, it is very unlikely that they have expectations about the potential influence of variations in the surgical methods on outcome. SCNs collecting outcomes in hospital or during follow-up after discharge will not know the surgical methods used; assessors grading CT scans (i.e. assigning an EHS class and 'scoring' other anatomical signs of PSH) will also not know the surgical methods used.

## vii. Bias in selection of the reported result (reporting bias)

Bias in selection of the reported results will be minimised by: (a) registering the study, including a description of the key elements of the research questions being addressed, on a publicly accessible registry (e.g. ISRCTN); (b) finalising a detailed statistical analysis plan (SAP) before locking the database for the study; (c) adhering to the SAP wherever possible and documenting any deviations with reasons when deviations are required due to unforeseen circumstances.

## 5. Study methods

## 5.1 Participant recruitment

The care of patients undergoing large and small bowel elective surgery for cancer or for inflammatory bowel disease is co-ordinated in all centres by specialist multi-disciplinary teams (MDTs). The MDTs meet regularly and consider all patients on the basis of their relevant staging investigations and other assessments. As part of usual care, a SCN or a surgeon will meet a patient identified by the MDT as requiring resection and stoma formation before surgery. The SCN or surgeon will give information about the study (patient information leaflet, PIL) to potential participants. Patients will be given as long as possible to consider the study before being approached for consent (at least 24 hours for elective surgery and usually more than 24 hours for expedited surgery). On rare occasions when a theatre becomes unexpectedly available, patients undergoing expedited surgery may be asked for consent less than 24 hours after receiving information about the study. SCNs approaching patients will not consent a patient if he/she requests longer thinking time and this was not available; patients who are visibly distressed will not be approached for consent.

Patients may be consented retrospectively following their surgery, as well as prospectively. Retrospective consent will be sought from eligible patients when consent cannot be obtained preoperatively for example: when a final decision to form a stoma is not made until the patient is in theatre; and when there is not enough time to discuss or for patients to consider the study fully prior to surgery. Wherever possible, the patient will be informed about the study prior to their surgery.

We aim to recruit at least 70 NHS Trusts over a 12 month period. Participants will be recruited over 24 months. We anticipate that about 12000 patients will be screened during

this period, that 66% (n  $\approx$  8000) will be eligible and that 50% (n  $\approx$  4000) of eligible patients will consent to take part in the study. This equates to a recruitment rate of about 4 patients per centre / per month, although this average number will vary according to the workload of a centre. The proposed schema is shown in **Figure 1**.

## 5.2 Research procedures

Patients will undergo stoma formation in accordance with the techniques habitually used by each participating surgeon. The details of the procedure and aftercare will be at the discretion of the surgeon and in accordance with usual practice at each participating centre.

Research procedures for the purposes of the study only include:

- Provision of study information, review of the eligibility criteria and invitation to eligible patients to consent;
- Collection of key baseline, intraoperative and post-operative data for participants;
- Completion by participants of follow-up questionnaires, at the intervals specified in Table 3;
- Requests for participants' CT scans carried out in the course of usual care during the follow-up period.

## 5.3 Definition of end of study

Patients who consent to the study will be followed-up with patient questionnaires for a minimum of 2 years post-operatively. The end of the study will be the point in time when the last participant enrolled completes their 2 year questionnaires, all database queries have been resolved and the database has been locked.

#### 5.4 Data collection

Data will be captured in a purpose-designed secure database. Data required for the cohort study will be collected at different times (and by different people; see **Figure 2**). Additional details of specific data items are shown in **Table 4**.

#### Figure 2: Data Collection Diagram

#### Footnotes:

- 1. SCNs will record the number of visits at 6 weeks, 6 months and 6 monthly thereafter; we also intend to obtain these data from the database used locally.
- 2. We intend to obtain data for all visits from the database used locally.
- 3. HES and ONS data should record all hospital activity but will only be extracted periodically.

	Time / frequency of data collection with respect to date of index surgery						
	Before	During	Up to discharge	6-weeks after	6-month after	12-month after	6-monthly to study end
Screening log	~						
Consent form	~						
Participant baseline details	~						
Surgical details		~					
Complications			~				
Index hospitalisation resource use		~	~				
SCN contacts with participants and hospital admissions				~	~	~	~
Exercise, support garment data				~	~	~	
EQ-5D-5L; SF-12	~			~	~	~	~
Wound questionnaire			~	~			
Community-based health care					~	~	~
Stoma questionnaire					~	~	~
Questionnaire about living with a stoma						~	
Request CT scans, taken as part of patient's usual care				~	~	~	~
Stoma care products issued				~	~	~	~
In-patient hospital episodes *					~	~	~
Out-patient hospital episodes *					~	~	~

## Table 4:Timing and frequency of collection of data items

Footnotes:

\*In-patient and out-patient hospital episodes will be extracted from HES data, which will be requested periodically throughout the study.

Data collection will include the following elements:

- (a) A screening log of patients undergoing elective surgery to form a stoma. This log will be maintained by centres but data from the log will only be entered for eligible patients who consent to take part in the study (i.e. participants).
- (b) Confirmation of patient's eligibility against all eligibility criteria, written informed consent and patient's contact preferences (see below).
- (c) Baseline data characterising participants before surgery will be collected by the SCNs and obtained retrospectively from a HES data extract. Data from these sources will include any relevant diseases and comorbidities the participant may have and their current health status.
- (d) Surgery details will be collected by the surgical team in theatre and entered into an online database. These details will describe how the stoma is formed.
- (e) Details of a participant's recovery after surgery will be collected at discharge by the SCNs and obtained retrospectively from a HES data extract. These details will describe the patients post-operative stay including surgical or medical complications.
- (f) All follow up contacts between a participant and a SCN will be recorded by the SCNs; we also intend to obtain these details from local NHS stoma care databases used by hospitals when available.
- (g) Participants will be asked to complete health questionnaires, i.e. the EQ-5D-5L and SF-12, a purpose-designed questionnaire about stoma symptoms developed in Phase A [34], a questionnaire about how the participant is adapting to living with a stoma [43] and brief questions about primary care, social care and other resource use related to the stoma. Participants will be able to choose to receive the questionnaires by post or to complete them via an online secure website. Subject to their consent, we may also issue reminders to participants about completing questionnaires by text messaging.
- (h) CT scan images performed during the patient's involvement in the study will be obtained through the image exchange portal. These images will be assessed by surgical trainees using the European Hernia Society (EHS) classification system (see Figure 3). Our intention is to review at least one CT scan during each year of followup. The frequency of CT scans may also indicate that a participant has a health problem and the coordinating team will monitor this. A CT scan taken less than 2 weeks after the previous scan will not be requested for assessment.
- (i) Information about in-patient hospital episodes and out-patient hospital episodes will be obtained from periodic linked extracts of Hospital Episode Statistics (HES) data, from NHS Digital.
- (j) Information about participants who die during the study will be obtained from the periodic linked data extracts from the Office of National Statistics (ONS).
- (k) Information about resource use will be collected from participants directly (to record primary and social care use), from routinely collected data sources, e.g. NHS Digital (hospital episode statistics) and database used locally to record SCN visits and stoma care products issued.

#### 5.5 Assessment of CT scans

Volunteer surgical trainees (members of Surgical Trainee Collaboratives, STCs) will be recruited to assess CT scans (see 6). They will be trained (see 7) to grade CT scans using the EHS PSH classification and to assess other features; as part of training, a trainee will have to pass a performance assessment, comparing his/her grading with the grading of an expert. The process by which such patients and their scans will be identified and managed is described in **Figure 3**.

CT scan grading by trainees will be carried out in duplicate, using a web application developed for the study. CT scans will be viewed through the IEP (CIPHER 'node' hosted by Sectra Ltd, provider of the IEP to the NHS in the UK). EHS classifications that differ by ≥2 EHS grades will be adjudicated by an expert adjudicator. Duplicate grading will also provide information about the reproducibility of all graded features.

The features to be graded are:

- incisional hernia visible (Y/N)
- maximal axial diameter of the trephine (cm/mm)
- maximal craniocaudal diameter of the trephine (cm/mm)
- type of tissue involved in the hernia
- volume of tissue involved in the hernia
- amongst other things.

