#### 4.6 Primary and secondary outcomes

#### 4.6.1 Primary outcome

The primary outcome will be PSH incidence during follow-up after index surgery to form a stoma. An incident PSH is defined as:

- Symptoms of PSH (see 5.4), and
- Anatomical PSH, ascertained by independent reading of a CT scan (6)

Participants will describe their PSH symptoms using a custom-designed questionnaire, the "stoma questionnaire" [34]. Symptoms will be classified as green (asymptomatic), amber (mild/moderate symptoms) or red (severe symptoms). Cut-off points for these classifications will be defined on the basis of on-going data collection. We anticipate that severe symptoms may include recurrent problems with the stoma appliance, pain, or admission to hospital with obstruction. Mild/moderate symptoms are likely to be associated with discomfort and ill-fitting appliance issues managed by the patients themselves.

CT scans carried out in the course of a patient's usual NHS care will be assessed for all participants, with anatomical PSH being graded using the EHS classification (EHS class I, II, III or IV [24]). CT scans taken up to 6 months before or 3 months after the stoma questionnaire is completed will be valid for assessing anatomical PSH. The combination of symptomatic PSH and anatomical PSH confirmed by CT imaging will be our primary outcome. CT assessors will collect additional details from CTs (e.g. linear measurement of the PSH defect rather than just defect size >5cm vs ≤5cm), including a measure of the size of the PSH. The ESH criteria for classifying PSH as small or large will be reviewed on the basis of these additional data as the study progresses.

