#### 7. Training infrastructure for STCs

It will be necessary to train surgical trainees to assess the CT scans. Therefore, this protocol also describes the infrastructure we propose to establish to do this, since infrastructure does not exist outside the study and is required for it.

A selection of identifiable CT scans from patients with stomata have been obtained with consent by the Chief Investigator for a previous study and researchers carrying out Phase A of the CIPHER study. We will write to patients who gave permission for their CT scans to be

used previously and ask their consent to use their scans in the CIPHER study to train volunteer trainees to grade CT scans. All scans for which patients give their consent will be submitted to the CIPHER 'node' hosted by Sectra Ltd.

Trainees will be directed to view a training video to learn about the feature they are required to grade and how to use the CIPHER web application to record their assessments. The training CT scans will be able to be viewed through the IEP, just like CT scans obtained for participants in the main cohort. A range of training scans will be queued for assessment by a trainee. When the trainee is confident about carrying out the grading, he/she will be able to request the CTEU to queue a set of training CT scans. In order to be accepted as a grader for the main cohort study, a trainee will have to achieve 90% accuracy in assigning EHS PSH class, compared to the class assigned by an expert grader.

This group of patients will be similar to those recruited to the prospective cohort (having undergone stomata formation at our Cl's institution) and will be approach for their consent to use their images for the purposes of STC training and assessment. A patient information leaflet will explain the study and will be sent to patients along with a postal consent form. However, a PIL and consent form will only be sent to patients, once we have confirmed their survival status on NHS Spine. This is essential because the majority of this cohort have undergone bowel resection for cancer.

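### The CT adjudication trigger (a gap of at least two EHS grades) is not set at the present/absent boundary that decides the primary outcome, so a 'no PSH' versus class I split is not sent to the expert

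*Protocol*

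**What the plan says.** Section 5.5 of the Phase B protocol sets up double reading: "CT scan grading by trainees will be carried out in duplicate, using a web application developed for the study". It gives one rule for disagreements: "EHS classifications that differ by ≥2 EHS grades will be adjudicated by an expert adjudicator". The only other stated use of the second reading is descriptive: "Duplicate grading will also provide information about the reproducibility of all graded features".

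Section 4.6.1 defines the imaging half of the primary outcome as "Anatomical PSH, ascertained by independent reading of a CT scan", and then states: "The combination of symptomatic PSH and anatomical PSH confirmed by CT imaging will be our primary outcome". Hernias are graded in EHS classes I to IV, and a hernia of any class counts. 'No PSH' is given no number on that scale. Section 8.1 places the event at the time imaging confirms the hernia.

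Readers are volunteer surgical trainees. To be accepted under section 7, "a trainee will have to achieve 90% accuracy in assigning EHS PSH class", judged against an expert. Section 4.8 (vi) says that CT assessors will not know the surgical method used.

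**The concern.** For the primary outcome the CT answers one question: is there a PSH or not? The trigger measures something else, the distance between two grades. Two readers who record class I and class III agree that a hernia is present, so their disagreement cannot change the event, yet it goes to the expert. Two readers who record no hernia and class I disagree on exactly the point that decides the event, and the trigger does not pick this up.

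Such a scan must still become event or no event. If no expert reading exists, a default has to do it: either reader positive, both positive, or one designated reader. Each default carries reader error that the planned adjudicator could have removed. At stake are the incidence in objective 1, the hazard ratios for surgical technique, and the event date, since that is the date of imaging confirmation.

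**Working it through.** **Step 1: which disagreements the trigger reaches.** The protocol gives no figure to reproduce here, so this is a logic check. Assume none = 0, I = 1, II = 2, III = 3, IV = 4; placing 'none' at 0 is an assumption. There are 10 discordant pairs.

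| Pair | Gap | To expert? | Changes PSH yes/no? |
|---|---|---|---|
| none/I | 1 | no | **yes** |
| none/II | 2 | yes | yes |
| none/III | 3 | yes | yes |
| none/IV | 4 | yes | yes |
| I/II, II/III, III/IV | 1 | no | no |
| I/III, II/IV | 2 | yes | no |
| I/IV | 3 | yes | no |

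The rule covers 3 of the 4 outcome-changing pairs and misses none/I. If 'none' is not an EHS grade, it has no grade distance from any class and the rule covers 0 of 4. On either reading, I/III, I/IV and II/IV go to the expert although they cannot change the event.

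**Step 2: a bound for CT alone.** Assumptions: each reader is right on presence or absence with probability a; errors are independent and unrelated to surgical technique; no discordant scan is adjudicated; true risks are 30% and 20%. The value a = 0.90 borrows the section 7 pass mark, which is set for class.

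- Discordant on presence: 2a(1 − a). At 0.90 this is 2 × 0.9 × 0.1 = 18%; at 0.95 it is 2 × 0.95 × 0.05 = 9.5%.
- 'Either' rule: sensitivity 1 − (1 − a)², specificity a². 'Both' rule: sensitivity a², specificity 1 − (1 − a)². One reader: both equal a.
- Observed risk: q = sens × p + (1 − spec) × (1 − p).
- Observed HR: ln(1 − q₁)/ln(1 − q₀). With no error, ln 0.70/ln 0.80 = 0.3567/0.2231 = 1.60.

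| Accuracy | Default | q at 30% | q at 20% | Observed HR |
|---|---|---|---|---|
| 90% | either | 0.99×0.30 + 0.19×0.70 = 0.430 | 0.99×0.20 + 0.19×0.80 = 0.350 | 0.5621/0.4308 = 1.30 |
| 90% | one reader | 0.90×0.30 + 0.10×0.70 = 0.340 | 0.90×0.20 + 0.10×0.80 = 0.260 | 1.38 |
| 90% | both | 0.81×0.30 + 0.01×0.70 = 0.250 | 0.81×0.20 + 0.01×0.80 = 0.170 | 1.54 |
| 95% | either | 0.9975×0.30 + 0.0975×0.70 = 0.3675 | 0.9975×0.20 + 0.0975×0.80 = 0.2775 | 1.41 |
| 95% | both | 0.9025×0.30 + 0.0025×0.70 = 0.2725 | 0.9025×0.20 + 0.0025×0.80 = 0.1825 | 1.58 |

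With an error-free expert on every present/absent split, sensitivity and specificity at 90% accuracy are both 0.99. Then q is 0.304 and 0.206, and the HR is 1.57.

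**Step 3: closer to the real endpoint.** The event also requires symptoms. Take 75% of hernias as symptomatic (section 2.2.1, given there as a minimum) and assume 30% of hernia-free participants report qualifying symptoms (range 10% to 50%). The true composite risks are 0.75 × 0.30 = 0.225 and 0.75 × 0.20 = 0.150, so the HR is ln 0.775/ln 0.850 = 1.57. At 90% accuracy under 'either':

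- q₁ = 0.75×0.30×0.99 + 0.30×0.70×0.19 = 0.2627
- q₀ = 0.75×0.20×0.99 + 0.30×0.80×0.19 = 0.1941
- HR = 1.41 (1.51 at 10% symptomatic, 1.34 at 50%)

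Under 'both' it is 1.54 (1.55 to 1.53). If half the discordant scans also reach the expert (assumption), 'either' gives specificity 0.81 + 0.09 = 0.90 and an HR of 1.48 (1.53 to 1.43).

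**The case against.** Four points can be made for the plan.

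- **A rule may exist elsewhere.** Section 5.5 refers to Figure 3 for how scans are managed. That figure is not in the text available, and the SAP may say which reading is analysed. This stands: a reader might infer that none/I splits are never resolved, and the documents do not support that. It does not remove the point. Section 5.5 itself fixes the trigger, and an analysis default chosen later does not supply an expert reading that was never requested. Stored duplicate readings would allow re-adjudication before database lock, so the gap is recoverable, but only if someone plans for it.
- **The trigger is not blind to presence and absence.** With 'none' as grade 0 it catches three of the four relevant pairs. This stands. A reader might infer that the expert is used only on disagreements that do not matter; on that scale this is wrong.
- **The large figures overstate the effect.** A reader might take 18% discordance and an HR falling from 1.60 to 1.30 as the effect of this rule. They treat all discordance as unadjudicated, apply a class pass mark to presence (confusing I with II fails the mark but not presence) and ignore the symptom requirement. This stands.
- **Readers are trained, tested and blind to technique.** This also stands. It points to non-differential error, so attenuation and shifted incidence are expected more than bias for or against a technique.

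**Conclusion.** The concern holds in a limited form. The protocol states an adjudication rule whose threshold does not match the outcome it serves. Depending on where 'no PSH' sits, the rule misses one of the four outcome-changing disagreements or all four, and no rule in the visible text settles those it misses.

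The effect falls on symptomatic participants with a CT in the permitted window. Its size cannot be determined, because the share of none/I splits is not given. For CT alone, 1.60 seen as 1.30 is a worst case (90% accuracy, 'either', no adjudication); at 95% accuracy the range is 1.41 to 1.58. Adding the symptom requirement at 90% accuracy gives about 1.41 to 1.54 against a true 1.57. All these figures assume independent, non-differential reader error and true hernia risks of 30% and 20%; the composite figures also rest on the symptom rates in Step 3. This is a should-fix: a mismatch in a stated rule, with a cheap and complete remedy.

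**What to change.** In section 5.5, keep the existing trigger and add, for example: Every scan on which the two graders disagree on PSH present versus absent (none versus any EHS class) is also adjudicated by the expert, and the adjudicated reading is used for the primary outcome. State in the same place where 'no PSH' sits on the grading scale, and check that Figure 3 and the web application agree.

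The class-distance trigger should stay. Section 4.6.1 plans to review the small/large size criteria using the additional CT data, so class disagreements still matter for that work.

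The cost is a short text change, one more condition in the web application, and somewhat more scans for the adjudicator already planned. Sample size, scanning and participant burden do not change. Scans already read in duplicate can be checked against the new condition from the stored readings.
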